1.4. Statistical Analyses

1.4.1. General Considerations

The statistical analyses will be performed under the responsibility of the Sponsor’s Biostatistics platform using SAS® Version 9.4 or later.

For descriptive purposes, the following statistics will be presented:

Table 3.2: Descriptive statistics produced

Disposition and follow-up description	Categorical data	At least number of subjects (Percentage of subjects are also possible).
	Continuous data	Mean, standard deviation, [quartiles,] minimum and maximum.
Baseline characteristics	Categorical data	Number of subjects. Percentage of subjects.
	Continuous data	Mean, standard deviation, quartiles, minimum and maximum.
Clinical safety results	Categorical data	Solicited: Number and percentage (95% CIs for main endpoints) of subjects. Unsolicited: Number and percentage (95% CIs for main endpoints) of subjects and number of events.
Immunogenicity results	Categorical data (seroprotection, cutoff)	Number and percentage (95% CIs for main endpoints) of subjects.
	Continuous data (titer / data)	Log10: Mean and standard deviation. Anti-Log10 (work on Log10 distribution, and anti-Log10 applied): Geometric mean, 95% CI of the geometric mean, quartiles, minimum, and maximum.

		Graphical representation by Reverse Cumulative Distribution Curve (RCDC).
--	--	---

The confidence interval (CI) for the single proportion will be calculated using the exact binomial method (Clopper-Pearson method, quoted by Newcombe (1), i.e., using the inverse of the beta integral with SAS®.

For immunogenicity results, assuming that Log10 transformation of the titers / data follows a normal distribution, at first, the mean and the 95% CI will be calculated on Log10 (titers / data) using the usual calculation for normal distribution (using Student's t distribution with n-1 degree of freedom), then antilog transformations will be applied to the results of calculations, in order to provide geometric means (GMs) and their 95% CI.

1.4.2. Primary Endpoint

Thirty days after the administration of the MenACYW conjugate vaccine (approximately 5 years after priming as toddlers), the sufficiency of the percentages of participants in Group 1 who achieve an hSBA vaccine seroresponse (see definition below) for meningococcal serogroups A, C, W, and Y will be tested.

Seroresponse will be considered sufficient if lower limit of the 1-sided 97.5% CI calculated using the Exact method (Clopper-Pearson method) for percentage of participants with hSBA seroresponse against serogroups A, C, W and Y is greater than 75%.

This is equivalent to testing $H_0: p \leq 0.75$ against $H_1: p > 0.75$, where p is the observed proportion of subjects with hSBA seroresponse against serogroups A, C, W and Y. The CI for the single proportion will be calculated using the exact method (Clopper-Pearson method).

Note: hSBA vaccine seroresponse for serogroups A, C, W, and Y is defined as:

- For a subject with a pre-vaccination titer < 1:8, the post-vaccination titer must be $\geq 1:16$
- For a subject with a pre-vaccination titer $\geq 1:8$, the post-vaccination titer must be at least 4-fold greater than the pre-vaccination titer

1.4.3. Secondary Endpoints

Immunogenicity

All analyses for the secondary endpoints will be descriptive; no hypotheses will be tested. Descriptive statistics will be provided for the hSBA and rSBA antibody titers against meningococcal serogroups (A, C, W, and Y) and for antibody concentrations against tetanus toxoid contained in MenACYW conjugate vaccine as a carrier protein. The results will be expressed as vaccine seroresponse, seroprotection, GMTs, and titers greater or equal to a specific threshold.

In general, categorical variables will be summarized and presented by frequency counts, proportion percentages, and CIs. The 95% CIs of point estimates will be calculated using the normal approximation for quantitative data and the exact binomial distribution (Clopper-Pearson

method) for percentages. For GMTs, 95% CIs of point estimates will be calculated using normal approximation assuming they are log-normally distributed.

Reverse cumulative distribution curve (RCDC) figures will be provided for the antibody titers against meningococcal serogroups and the antibody concentrations against tetanus toxoid contained in MenACYW conjugate vaccine.

In summary, descriptive analyses of antibody responses to A, C, W, and Y serogroups for Group 1 (at V1 [baseline], V2 [30 days after the administration of a booster dose of MenACYW conjugate vaccine], and at V3 before the administration of a booster dose), V4 (30 days after the administration of a booster dose of MenACYW conjugate vaccine), and for Group 2 at V2 before the administration of a booster dose of MenACYW conjugate vaccine and at V3 (30 days after the administration of a booster dose of MenACYW conjugate vaccine) will include but not be limited to:

- hSBA and rSBA seroprotection rate (titer \geq 1:8) and 95% CI
- hSBA and rSBA GMTs and 95% CI
- hSBA and rSBA titer distribution and RCDC
- Percentage of participants with hSBA titer \geq 1:4 and \geq 1:8 and 95% CI
- Percentage of participants with rSBA titer \geq 1:8 and \geq 1:128 and 95% CI
- Percentage of participants with hSBA and rSBA titer \geq 4-fold rise from pre-vaccination to post-vaccination, and 95% CI
- Percentage of participants with hSBA and rSBA vaccine seroresponse rate and 95% CI

hSBA vaccine seroresponse for serogroups A, C, W, and Y is defined as:

- For a participant with a pre-vaccination titer $<$ 1:8, the post-vaccination titer must be \geq 1:16
- For a participant with a pre-vaccination titer \geq 1:8, the post-vaccination titer must be at least 4-fold greater than the pre-vaccination titer

rSBA vaccine seroresponse for serogroups A, C, W, and Y is defined as:

- A post-vaccination rSBA titer \geq 1:32 for participants with pre-vaccination rSBA titer $<$ 1:8, or
- A post-vaccination titer \geq 4 times the pre-vaccination titer for participants with pre-vaccination rSBA titer \geq 1:8

The hSBA and rSBA antibody titers against serogroup C will also be described for Group 1 at V1 (baseline) and V2 (30 days after the administration of a 5-year booster dose of MenACYW conjugate vaccine, and at V3 and V4 (30 days after administration of the second booster dose of MenACYW conjugate vaccine), and for Group 2 at V2 and V3 (30 days after administration of a 10-year booster dose of MenACYW conjugate vaccine) according to the priming status in infancy before receiving the toddler dose in MET51 study (meningococcal vaccine naïve or MenC-primed).

In addition, descriptive analyses on anti-tetanus antibody concentrations for Group 1 at V1 (baseline) and V2 (30 days after the administration of a 5-year booster dose of MenACYW conjugate vaccine, and at V3 and V4 (30 days after administration of the second booster dose of MenACYW conjugate vaccine, and for Group 2 at V2 and V3 (30 days after administration of a 10-year booster dose of MenACYW conjugate vaccine) will include but not be limited to:

- GMCs and 95% CI
- The percentage of participants with antibody concentrations to tetanus toxoid ≥ 0.01 IU/mL and ≥ 0.1 IU/mL and 95% CI

Data from MET51 and MEQ00073 will also be combined and paired (data at baseline will be pooled for Group 1 and Group 2 for 5-years persistence after priming in MET51) to evaluate antibody persistence and overall trends over 5 and 10 years. Kinetic curves will also be presented to describe persistence.

In addition, immunogenicity will be described according to sex, as appropriate according to number of participants in the respective subgroups. Subgroup analyses will be performed on PPAS.

Safety

Safety results will be described for participants in the study. The main parameters for the safety endpoints will be described by 95% CIs (based on the Clopper-Pearson method).

Depending on the items, the endpoints recorded or derived could include: nature (Medical Dictionary for Regulatory Activities [MedDRA] preferred term), time of onset, duration/number of days of occurrence, intensity, relationship to the vaccine, whether the AE led to early termination from the study, outcome, and seriousness criterion.

In addition, the main safety endpoints will be described according to sex , as appropriate according to number of participants in the respective subgroups.

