Table 2.1 shows a comparison of the bactericidal antibody responses to MenACYW conjugate vaccine and Nimenrix vaccine 30 days after the vaccination of meningococcal vaccine naïve subjects only or combined (naïve + MenC-primed) subjects 12 through 23 months of age.

Table 2.1: Comparison of bactericidal antibody responses to MenACYW conjugate vaccine and Nimenrix Vaccine Reported in MET51

Endpoint by Serogroup	MenACYW (95% CI) Naïve	Nimenrix vaccine (95% CI) Naïve	MenACYW (95% CI) Combined (Naïve + MenC Primed)	Nimenrix vaccine (95% CI) Combined (Naïve + MenC Primed)
A	N=293	N=295	N=490	N=393-394
% ≥ 1:8 (Seroprotection)**	90.8 (86.9; 93.8)	89.5 (85.4; 92.7)	90.4 (87.4; 92.9)	91.6 (88.4; 94.2)
% Seroresponse	76.8 (71.5; 81.5)	72.5 (67.1; 77.6)	76.5 (72.5; 80.2)	77.1 (72.6; 81.2)
hSBA GMT	28.7 (25.2; 32.6)	28.0 (24.4; 32.1)	29.9 (26.9; 33.2)	34.5 (30.5; 39.0)
C	N=293	N=295	N=489	N=393-394
% ≥ 1:8 (Seroprotection)**	99.3 (97.6; 99.9)	81.4 (76.4; 85.6)	99.2 (97.9; 99.8)	85.5 (81.7; 88.9)
% Seroresponse	98.3 (96.1; 99.4)	71.5 (66.0; 76.6)	97.1 (95.2; 98.4)	77.4 (72.9; 81.4)
hSBA GMT	436 (380; 500)	26.4 (22.5; 31.0)	880 (748; 1035)	77.1 (60.7; 98.0)

Endpoint by Serogroup	MenACYW (95% CI) Naïve	Nimenrix vaccine (95% CI) Naïve	MenACYW (95% CI) Combined (Naïve + MenC Primed)	Nimenrix vaccine (95% CI) Combined (Naïve + MenC Primed)
W	N=293	N=296	N=489	N=393-394
% ≥ 1:8 (Seroprotection)**	83.6 (78.9; 87.7)	83.4 (78.7; 87.5)	84.9 (81.4; 87.9)	84.0 (80.0; 87.5)
% Seroresponse	67.6 (61.9; 72.9)	66.6 (60.9; 71.9)	70.8 (66.5; 74.8)	68.4 (63.6; 73.0)
hSBA GMT	22.0 (18.9; 25.5)	16.4 (14.4; 18.6)	24.4 (21.8; 27.5)	17.7 (15.8; 19.8)
Y	N=293	N=296	N=488-490	N=394-395
% ≥ 1:8 (Seroprotection)**	93.2 (89.7; 95.8)	91.6 (87.8; 94.5)	94.3 (91.8; 96.2)	91.6 (88.5; 94.2)
% Seroresponse	81.9 (77.0; 86.1)	79.1 (74.0; 83.5)	84.8 (81.3; 87.9)	78.9 (74.6; 82.9)
hSBA GMT	38.0 (33.0; 43.9)	32.2 (28.0; 37.0)	41.7 (37.5; 46.5)	31.9 (28.4; 36.0)

N: number of subjects in the per-protocol analysis set

95% CI of the single proportion calculated from the exact binomial method.

** Non-inferiority criterion met

Toddlers who received monovalent MenC vaccination during infancy

The GMTRs were 0.496 (with the upper bound of the 95% CI lower than 1.0) for serogroup A, 1.34 and 1.29 (with the lower bound of the 95% CI below 1.0) for serogroups C and W, respectively, and 1.53 (with the lower bound of the 95% CI greater than 1.0) for serogroup Y.

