Response in toddlers previously vaccinated with MenC conjugate vaccines in their first year of life

The majority of monovalent MenC-primed toddlers (12 to 23 months of age) in study MET51 (NCT02955797) had hSBA titers ≥ 1:8 in the MenQuadfi group (N=198) (≥ 86.7%) and in MenACWY-TT group (N=99) (≥ 85.7%) at D30 post-vaccination. These toddlers received during their infancy MenC-TT or MenC-CRM vaccines. Post-vaccination seroprotection rates were comparable between MenQuadfi and MenACWY-TT for all serogroups regardless of the priming background.

In MenC-CRM-primed toddlers, the GMTs for serogroup A were lower in the MenQuadfi group (n=49) than in the MenACWY-TT group (n=25) (12.0 [8.23; 17.5] vs 42.2 [25.9; 68.8]). After administration of MenQuadfi, seroprotection rates (hSBA titers ≥ 1:8) for toddlers primed with MenC-CRM were lower but still comparable for serogroups A, Y and W compared with those in the MenACWY-TT group (A: 68.8% [53.7; 81.3] vs 96.0% [79.6; 99.9]; Y: 95.8% [85.7; 99.5] vs

80.0% [59.3; 93.2]; W: 68.1% [52.9; 80.9] vs 79.2% [57.8; 92.9]). The rates for serogroup C were comparable in both groups (95.7% [85.5; 99.5] vs 92.0% [74.0; 99.0]). The clinical relevance of these results is unknown. This aspect might be considered for individuals at high risk for MenA infection who received MenC-CRM vaccine in their first year of life.

Antibody Responses (serum bactericidal assay using baby rabbit complement [rSBA] GMTs and Titers \geq 1:8) at D30

Toddlers who either were meningococcal vaccine naïve or had received monovalent MenC vaccination during infancy

At D30, meningococcal rSBA GMTs were lower in MenACYW recipients than in Nimenrix vaccine recipients for serogroup A (1382 and 4882, respectively), and higher in MenACYW recipients than in Nimenrix vaccine recipients for serogroup C (2150 and 686, respectively).

Thirty days after vaccination, the percentages of participants with rSBA antibody titers \geq 1:8 were high and comparable between MenACYW and Nimenrix vaccine recipients ranging from 97.3% to 100.0% for all serogroups.

Other relevant Phase II and Phase III studies that concern the toddler populations are discussed below.

MET62

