Group 1. With this amendment, the boostability of MenACYW conjugate vaccine will also be described in adolescents primed with MenACYW conjugate vaccine approximately 10 years earlier as toddlers (Group 2) and in adolescents boosted as children approximately 5 years earlier (after priming at toddler age [Group 1]). The persistence of the immune response against meningococcal serogroups A, C, W, and Y in adolescents approximately 10 years after the primary vaccination as toddlers (Group 2) and in adolescents approximately 5 years after a booster dose administered as children (approximately 5 years after priming at toddler age [Group 1]) will be described.

MenC titers will also be described according to the priming status in infancy before receiving the toddler dose in MET51 study (meningococcal vaccine naïve or MenC-primed).

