1.8.5.5. MenC primed status

Participants who have received monovalent MenC vaccination during infancy are considered as “Primed” whereas participants who haven’t received monovalent MenC vaccination during infancy is considered as “Naïve”. The MenC primed status is defined according to the priming status in infancy before receiving the toddler dose in MET51 study

5. Changes in the Conduct of the Trial or Planned Analyses

Not applicable.

6. Supporting Documentation

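### Should the plan have described serogroups A and W by the carrier of the infant MenC vaccine, and not only serogroup C by primed or naive status?

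*SAP*

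**What the plan says.** Every place that plans results by infant priming status limits them to serogroup C. The objectives tables do so in Protocol 1.1 and 3 and in SAP section 2. Protocol 2.1 states: "MenC titers will also be described according to the priming status in infancy before receiving the toddler dose in MET51 study". Protocol 9.4.3.1 and SAP 1.4.3 carry the same analysis: "The hSBA and rSBA antibody titers against serogroup C will also be described for Group 1 at V1 (baseline) and V2". SAP 1.8.5.5 derives a two-level variable, Primed or Naïve: "The MenC primed status is defined according to the priming status in infancy before receiving the toddler dose in MET51 study". Neither document defines a MenC-TT or MenC-CRM category. The only other immunogenicity subgroup named in SAP 1.4.3 is sex.

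All secondary immunogenicity analyses are descriptive, and Protocol 9.4.3.1 and SAP 1.4.3 state that their lists of summaries are not exhaustive.

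The MET51 background in Protocol 2.1 says: "In MenC-CRM-primed toddlers, the GMTs for serogroup A were lower in the MenQuadfi group (n=49) than in the MenACWY-TT group (n=25"). It adds that "seroprotection rates (hSBA titers ≥ 1:8) for toddlers primed with MenC-CRM were lower but still comparable for serogroups A, Y and W" (its own Y figures, 95.8% against 80.0%, are in fact higher with MenACYW). It calls the clinical relevance unknown and remarks: "This aspect might be considered for individuals at high risk for MenA infection who received MenC-CRM vaccine in their first year of life".

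**The concern.** In CRM-primed toddlers serogroup C shows no deficit (95.7% against 92.0%), while serogroup A clearly does. So the planned breakdown covers the serogroup without a reported gap and leaves out the one with it.

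Extending the primed/naive split to A and W would not help either. In MET51 the CRM-primed minority is averaged away inside the primed group, which looks much like the naive group. Only a split by carrier would show it.

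Carrier was tabulated in MET51 (52 CRM and 151 TT among the primed MenACYW recipients), and the SAP already pairs MET51 with MEQ00073 data. The omission therefore looks cheap to repair. At stake would be a question that the protocol itself leaves open: whether children primed with MenC-CRM stay less well covered against serogroup A at 5 years and after a booster.

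**Working it through.** **1. The printed figures reproduce.** With r = 72 of 84 as the smallest count whose exact 97.5% lower limit exceeds 75%, power is 99.97% (A and Y), 92.6% (C) and 99.0% (W). The product is 91.6%, in line with Protocol Table 9.1. None of this depends on MenC carrier.

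The MET51 percentages and exact intervals correspond to these counts:

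| MenACYW recipients | A | W |
|---|---|---|
| Combined (Table 2.1) | 443/490 = 90.4% | 415/489 = 84.9% |
| Naive (Table 2.1) | 266/293 = 90.8% | 245/293 = 83.6% |
| Primed = combined − naive | 177/197 = 89.8% | 170/196 = 86.7% |
| CRM-primed (Protocol 2.1) | 33/48 = 68.8% | 32/47 = 68.1% |
| TT-primed = primed − CRM | 144/149 = 96.6% | 138/149 = 92.6% |

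The naive A row is printed as "90.8 (86.9; 93.8"). The derived 86.7% for W equals the minimum printed for all primed toddlers: "had hSBA titers ≥ 1:8 in the MenQuadfi group (N=198) (≥ 86.7"%). So the averaging effect is real. The TT row, however, is printed nowhere. It comes from rounded percentages and assumes that the CRM denominators of 48 and 47 are the ones inside Table 2.1.

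**2. Which difference is reported?** Protocol 2.1 compares the two vaccines within CRM-primed toddlers:

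- A: 33/48 against 24/25, Fisher p = 0.007.
- W: 32/47 against 19/24, p = 0.41.

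Inclusion criterion I01 admits only children who received MenACYW in MET51. There is no comparator arm to follow, so persistence of this difference is outside the study whatever tables are added.

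**3. Is CRM against TT the same signal?** By subtraction, the serogroup A GMTs are as follows.

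- MenACYW, primed: exp[(490 ln 29.9 − 293 ln 28.7)/197] = 31.8.
- MenACYW, TT-primed: exp[(197 ln 31.8 − 48 ln 12.0)/149] = 43.5, against 12.0 for CRM.
- Comparator, primed (combined N 394): exp[(394 ln 34.5 − 295 ln 28.0)/99] = 64.3.
- Comparator, TT-primed: exp[(99 ln 64.3 − 25 ln 42.2)/74] = about 74, against 42.2 for CRM.

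As a check, 31.8/64.3 = 0.49, against the printed primed GMTR of 0.496.

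The CRM-primed GMT is lower than the TT-primed GMT with both vaccines: 12.0/43.5 = 0.28 and 42.2/74 = 0.57. Part of the CRM–TT gap may therefore belong to the children or their country rather than to MenACYW. The deficit against the comparator is also not confined to CRM: 43.5/74 = 0.59 in TT-primed toddlers. For W, the printed GMTR in all primed toddlers is 1.29, in favour of MenACYW, with a lower bound below 1.

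**4. What could a carrier split show?** CRM-primed children were 52 of the 509 MenACYW recipients (306 + 203). If that mix holds:

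| Enrolment | CRM-primed | Example | Exact 95% CI |
|---|---|---|---|
| Both groups at V1, 500 (maximum) | 500 × 52/509 ≈ 51 | 36/51 | 56% to 83% |
| Group 1, 250 (maximum) | 250 × 52/509 ≈ 26 | 18/26 | 48% to 86% |
| Group 1, 125 (half of maximum) | 125 × 52/509 ≈ 13 | 9/13 | 39% to 91% |
| Group 1, 84 (size used for power) | 84 × 52/509 ≈ 9 | 6/9 | 30% to 93% |

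**5. Effect on the planned results.** Leaving the CRM subset out of the MET51 combined rates moves A from 90.4% to 410/442 = 92.8% and W from 84.9% to 383/442 = 86.7%. The whole-group summaries that the plan promises describe the enrolled population with or without a carrier table.

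**The case for a change.** The best case for the concern is this. The protocol raises the serogroup A result and calls its relevance unknown. Nothing in the text commits to looking at it again, and only a carrier split could show it. On the derived counts the CRM and TT intervals do not overlap (A 53.7% to 81.3% against 92.3% to 98.9%; W 52.9% to 80.9% against 87.2% to 96.3%). Two descriptive tables fixed in advance would cost little and would guard against selective reading later. At maximum enrolment, about 51 children at V1 would give an informative description.

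What stands: the reading of the text is right, the arithmetic is right, and a primed/naive split would hide the subset.

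What does not stand is the step from there to a fault in the plan. Prior MenC vaccination bears most directly on serogroup C, so that split is a coherent choice, and the documents apply it without contradiction. Choosing A and W for the extra tables would itself be selection from the MET51 results, and W rests on a derived rate alone. All primed children came from Hungary and Spain, and carrier by country is not given, so a carrier difference could be a country difference. The protocol's remark is about people at high risk of MenA infection. Exclusion criterion E07 keeps out children at high risk of meningococcal infection, and Protocol 2.2 describes serogroup A as minor in Europe. That the MET51 carrier field is available in the paired data is plausible but not stated.

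**Conclusion.** The concern does not hold. Followed as written, the plan answers each of its stated objectives, and none of them concerns MenC carrier. The primary test, its sample size and the serogroup C description are unaffected, and the documents agree with one another. What remains is a wish for one more descriptive subgroup. The non-exhaustive lists already permit it, and the table shells, which were not available for review, may or may not contain it.

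Such a subgroup could not follow the vaccine-against-vaccine difference that the protocol reports. It would follow a non-randomised CRM–TT contrast in about 26 Group 1 children at most, and about 9 at the 84 used for power. At the smaller size it could show neither that a gap persists nor that it has gone.

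This rests on three assumptions: the MET51 mix of 52 CRM in 509 carries over to enrolment, the counts recovered from rounded percentages are right, and the example rates stay near 70%. If nearly all eligible children enrolled, a gap as large as in MET51 might be visible at V1. That would make the table interesting, but it would not make its absence an error.

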1.4.4. Handling of Missing Data and Outliers

Generally, no replacement will be done for Safety Missing Data and Outliers.

1.4.4.1. Safety

1.4.4.1.1. Immediate

For unsolicited systemic AEs, a missing response to the “Immediate” field is assumed to have occurred after the 30-minute surveillance period and will not be imputed.

1.4.4.1.2. Causal Relationship

By convention, all events reported at the injection site (either solicited or unsolicited) will be considered as related to the administered product and then referred to as reactions. In a same way, all solicited systemic events pre-listed in the CRF are also considered as related to vaccination and will be considered as reactions.

- For unsolicited systemic AE, missing relationship will be considered as related to study vaccine at the time of analysis.
- The missing relationship to study procedures for SAEs will not be imputed.

1.4.4.1.3. Intensity

For solicited reactions, missing intensities will be handled as described in [Section 1.8.1.1.1](#). For unsolicited AEs, missing intensities will remain missing and will not be imputed.

1.4.4.1.4. Start Date and End Date

Missing or partially missing start dates or end dates for unsolicited AEs (including SAEs) will remain missing and not be imputed. If the start date is missing or partially missing, the time of onset will be considered to be missing. Nevertheless, unsolicited AEs with missing time of onset will be included in analyses according to the last vaccination (computed according to the [Section 1.8.1.2.3](#)). If either the start date or end date is missing or partially missing, the duration will be considered missing.

Missing or partially missing end dates for ongoing solicited AEs will remain missing and not be imputed.

